	Version: 2.0, 12SEP2021
	Page: 4 of 131

1.3 SPONSOR APPROVAL.

	Job title	DocuSign Stamp
Head of Global Clinical Operations	Senior Director Global Clinical Affairs	DocuSigned by: [name] Signer Name: [name] Signing Reason: I approve this document Signing Time: 13-Oct-2021 11:53:56 BST A32F12A80F1B4490986E80ACCB7471CB
Head of Global Clinical Strategy	Senior Director Global Clinical Strategies	DocuSigned by: [name] Signing Reason: I approve this document Signing Time: 14-Oct-2021 12:23:51 BST C809EF989A504C77BC7277E0F8E14B1D
Head of Global Biostatistics	Senior Director Global Data Analytics	DocuSigned by: Comparison of the Comparison o
Medical Affairs Representative	Vice President, Medical Affairs	DocuSigned by: July

Study Protocol	Smith-Nephew
A prospective, study to evaluate the safety and performance of PICO 14 in the management of acute and chronic wounds	Number: PICO14.WND.PRO.2019.03
	Version: 2.0, 12SEP2021
	Page: 5 of 131

2. SYNOPSIS.

Title of Study:	A prospective study to evaluate the safety and performance of PICO 14 in the management of acute and chronic wounds.	
Study Design:	ProspectiveMulti-centreNon-randomised	
Study Type:	Prospective, non-random, non-blinded case series.	
Study Product:	PICO 14.	
Comparison Group(s)*: (*if applicable)	There is no comparison group in this study.	
Study Purpose:	To generate evidence of the safe and effective use of the device in the management of chronic open wounds (pressure ulcers, venous leg ulcers, diabetes-related foot ulcers), dehisced surgical wounds and closed surgical incisions. The study comprises the PMCF for a new variant of an established product.	
Primary Objective:	To assess the functional performance of PICO 14 through verification of delivery of negative pressure and wound exudate management.	
	Closed incisions ONLY:	
	To assess clinical performance and safety of the PICO 14 NPWT system within 30 days of surgery through: • Incidence of Surgical Site Infection (SSI) – Superficial,	
Secondary Objective(s):	 Incidence of Surgical site Complications (SSC) [as applicable: dehiscence (superficial/deep etc.), seroma, necrosis, hematoma, suture abscess]. Condition of peri-wound skin assessed through visual inspection at 7, 14 and 30 days. Patient tolerability assessed by level of pain and level of satisfaction. 	

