It is clear that the patient populations intended to be exposed to PICO are very wide. These various populations are comprised of relatively healthy individuals with acute traumatic wounds through to patients with acute surgical wounds and/or patients with concomitant medical disorders, such as peripheral vascular disease and/or diabetes, particularly within the context of chronic wounds. Whilst a large segment of the patient population, especially in regard to chronic wounds, may be elderly, the proposed intended uses of PICO NPWT systems do not preclude patients of any particular age or demographic. Indeed, within the context of trauma, burn wounds and/or surgical wounds, it is realistic to anticipate that the clinical use of PICO NPWT systems will extend from childhood and adolescence, into adulthood and the elderly.

Overall, based on its intended clinical use PICO 14 is considered to be clinically interchangeable for the management of chronic wounds, acute wounds, traumatic wounds, sub-acute and dehisced wounds, ulcers (such as pressure or diabetic), partial thickness burns, flaps and grafts, and surgically closed incision wounds.

CONFIDENTIAL AND PROPRIETARY

Study Protocol—Device	Smith-Nephew
	Number: PICO14.WND.PRO.2019.03
management of courts and abronic wounds	Version: 2.0, 12Sep2021 Page: Page 29 of 131

Where a wound is proving difficult to heal, the typical approach is now often to try standard care (compression therapy, advanced wound dressings) first before progressing to more advanced techniques should this prove unsuccessful. Some of these advanced therapies are discussed below:

Despite analyzing 78 RCTs (7014 participants primarily women) in a Cochrane review and network systematic analysis of dressings, including silver, impregnated, and topical agents for treating VLUs, there was no certainty regarding which were most effective for healing86. In general, the studies had small numbers of patients per treatment and there was a high risk of bias.

Moues *et al* 2011129, in a systematic review of NPWT which identified more than 400 clinical papers and review articles, identified a single RCT in regard to the use of NPWT in VLUs and reported faster wound bed preparation times, faster median time to complete healing and better skin graft take rate in NPWT treated wounds. The authors noted the cost efficiency in favour of NPWT in this indication.

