Smith+Nephew's Global Biostatistics group will conduct the statistical analysis for this study. The subject data will be described and summarised using the baseline demographic and medical variables which include but are not limited to age, gender, ethnicity, medical and medication history, diagnostic factors as well as study process variables (e.g. AE and withdrawal(s)). Summary statistics will be given according to the nature of the variable, continuous or categorical. For continuous variables, the number of observations, mean, standard deviation, median, minimum, and maximum will be presented, while for categorical variables the number of observations, frequency, and percentages will be reported. Summary statistics will be presented by wound type and by country, where appropriate.

Primary, secondary, and exploratory outcome variables and derived variables will also be summarised accordingly. Parametric statistical tests will be used if the data is normally distributed and corresponding non-parametric tests will be considered if the data is not. Where necessary, suitable regression techniques will be used to adjust for confounding since the study is non-randomised. Unless otherwise stated, the results will be reported at 5% significance level and where appropriate 95% confidence intervals will be given.

11.2 ANALYSIS POPULATIONS.

- Full analysis set population (FAS), including all subjects who were recruited into the study and have at least one post-baseline visit.
- Safety Population (SAF), including all subjects who have received the study device.
- Per-Protocol Population (PP), including all subjects in the full analysis set who have no significant protocol deviations and met the inclusion/exclusion criteria.

Statistical analysis will be performed using each of the patient populations as follows: Analysis of the primary, secondary and exploratory efficacy objectives will be performed separately using both the Full Analysis Set and the Per Protocol Population. All safety analyses will utilize the Safety Population.

CONFIDENTIAL AND PROPRIETARY

Study Protocol—Device	Smith-Nephew
and performance of PICO 14 in the	Number: PICO14.WND.PRO.2019.03
	Version: 2.0, 12Sep2021 Page: Page 95 of 131
	rage 90 01 101

11.3 BASELINE DATA.

For chronic wounds and dehisced surgical wounds Day 0 (baseline) will be classified as the screening/ baseline visit. For closed surgical incisions Day 0 (baseline) will be classified as the operative day.

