The subjects will be described and summarised using the baseline demographic and medical variables which include but are not limited to age, gender, ethnicity, medical and medication history, diagnostic factors. Summary statistics will be given according to the nature of the variable; continuous or categorical.

11.4 EFFICACY ANALYSIS.

The study will assess and evaluate the efficacy of PICO 14 by establishing equivalence in the mean operating negative pressure over a period of 14 days with a pressure of -80.2 mmHg. The clinical efficacy of PICO 14 will be concluded if statistically significant equivalence (within an equivalence margin of ±6mmHg) is achieved. Secondary and exploratory outcomes will be evaluated to consolidate the primary outcome analysis.

The study is non-comparative and non-randomised, the impact of confounding on the measures of efficacy may be expected and will be evaluated through fitting appropriate models and adjusting for potential factors.

11.5 ANALYSIS OF PRIMARY ENDPOINT.

Delivery of -80mmHg negative pressure to the wound bed over the treatment period. This will be
measured by download of the built-in data chip from the PICO 14 devices to collect NPWT delivery
status.

The following hypotheses will be tested to establish equivalence of the PICO 14 integrated pump system compared to the literature value, with equivalence margin, δ_1 >0:

$$H_0: |\mu - \mu_0| \ge \delta_1$$

$$H_a$$
: $|\mu - \mu_0| < \delta_1$

In the stated hypotheses, μ represents the assumed mean operating pressure taken from data extracted from a PICO sample device (-80.2 mmHg) and μ_0 represents the mean PICO 14 pump operating pressure.

CONFIDENTIAL AND PROPRIETARY

Study Protocol—Device	Smith-Nephew
and performance of PICO 14 in the	Number: PICO14.WND.PRO.2019.03
	Version: 2.0, 12Sep2021
	Page: Page 96 of 131

The equivalence limit δ_1 = 6mmHg was chosen as a conservative non-clinically significant difference assuming that the difference is actually 0.

The average negative pressure across all subjects will be summarised as a continuous variable.

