The difference between the average negative pressure from baseline to treatment discontinuation and the assumed mean negative pressure (-80.2mmHg) will be calculated for each subject separately. This difference for closed incisions, dehisced surgical wounds and chronic wounds combined will be assessed using a two one-sided t-test at the alpha level of 0.025. The mean difference will be presented along with the associated 95% confidence interval and if the 95% confidence interval lies fully within the equivalence boundaries (-6; 6) then the null hypothesis is rejected and clinical equivalence will be confirmed.

As an additional analysis the above will be repeated separately for each wound indication.

 No occurrence of exudate leaks observed during the dressing wearing period resulting or not, in an unplanned dressing change.

Occurrence of exudate leaks in the opinion of the clinician will be recorded in the CRF. For non-occurrence of exudate leaks, a binary variable indicating presence of/absence of will be defined. For the combined group (closed surgical incisions, dehisced surgical wounds and chronic wounds) the frequency together with percentage of reported/identified outcome will be reported with a 95% CI. This will also be summarised separately for each wound indication.

Logistic models will be fitted and important associated factors adjusted for if there is adequate data.

Composite Clinical Success (CCS) defined as a binary variable (1/0) (1 if both of the following are true and 0 if either one is false):

- A. Nominal pressure is in the interval 80mmHg ± 6mmHg.
- B. No exudate leakage.

The CCS will be reported as a count and percentage with a 95% CI for the combined group and separately for each wound indication.

CONFIDENTIAL AND PROPRIETARY

Study Protocol—Device	Smith-Nephew
and performance of PICO 14 in the	Number: PICO14.WND.PRO.2019.03
	Version: 2.0, 12Sep2021
	Page: Page 97 of 131

11.6 ANALYSIS OF SECONDARY ENDPOINTS.

Closed Incision Only:

Clinical performance and safety of the PICO 14 NPWT system over a 14 day therapy and 30 day follow-up period to include:

- Scar quality measured by POSAS score at Day 14, and day 30.
- Incidence of Surgical Site Infection (SSI) and incidence of Surgical Site Complication (SSC) within 30 days of surgery [CDC criteria].
- Condition of peri-wound skin assessed through visual inspection at 7, 14 and 30 days.

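### Does the pooled ±6 mmHg test need a rule for what happens when a single wound indication is off target?

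*Combined protocol and SAP*

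**What the plan says.** Section 11.5 makes the pooled comparison primary: "This difference for closed incisions, dehisced surgical wounds and chronic wounds combined will be assessed using a two one-sided t-test". If the 95% confidence interval of the mean difference lies inside (-6; 6), "then the null hypothesis is rejected and clinical equivalence will be confirmed". Section 11.4 builds on this: "The clinical efficacy of PICO 14 will be concluded if statistically significant equivalence" is achieved within the margin, with no limit by indication.

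The by-indication pressure analysis is one sentence in 11.5: "As an additional analysis the above will be repeated separately for each wound indication". The same section also summarises exudate leaks by indication, and reports the composite success rate (pressure within 80 ± 6 mmHg and no leak) by indication with a 95% CI.

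Sections 7.1 and 11.10 list five wound types (pressure ulcer, venous leg ulcer, diabetes-related foot ulcer, dehisced surgical wound, closed incision), with at least 10 subjects in each and 70 in total. No maximum is set. On modelling, 11.1 says "suitable regression techniques will be used to adjust for confounding since the study is non-randomised", and 11.4 that "the impact of confounding on the measures of efficacy may be expected and will be evaluated through fitting appropriate models". Neither names a factor or a heterogeneity test. Section 11 describes itself as brief and defers detail to a SAP finalised before database lock.

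**The concern.** The Synopsis states the purpose wound by wound, beginning "To generate evidence of the safe and effective use of the device in the management of chronic open wounds" and going on to dehisced wounds and closed incisions. A pooled mean answers a different question: whether the average over the recruited mix is near -80.2 mmHg. A small deviant group can be diluted by the rest, and 11.4 would still conclude efficacy without qualification.

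The mix is also loose. Five minimums of 10 use 50 of the 70 places and leave 20 free, so closed incisions, for example, could number anywhere from 10 to 30. The same device could then pass or fail according to who was recruited.

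Section 6.1.1 gives some reason to expect differences between groups: dressing changes depend on wound type and exudate, and chronic and dehisced wounds may use two pumps over 28 days against 14 days for incisions. At stake is an efficacy statement, feeding the clinical evaluation report (5.5), that covers an indication where the device is outside its own margin.

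**Working it through.** **Inputs.** From 11.4, 11.5 and 11.10: margin 6 mmHg, alpha 0.025 for each one-sided test, SD 14.8, true difference 0, 55 evaluable subjects, 20% loss, 70 recruited. From 7.1: at least 10 per wound type. Assumed: a shift of 12 mmHg in one indication with all others on target, within-group SDs of 5, 8 and 10 beside 14.8, and normal data.

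**The plan's own figure.** The normal approximation is n = [SD × (z(1-α) + z(0.90)) / 6]². At α = 0.025 this is [14.8 × (1.960 + 1.282) / 6]² ≈ 64; the exact calculation gives 66, and 55 subjects give 67.9% power. The stated 55 fits α = 0.05 per side (exact minimum 54; 81.4% power at 55). That is a separate matter and does not affect this point.

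**Dilution by hand.** With a fraction f of subjects off by 12, the pooled shift is 12f and the total variance is SD² + 144 f(1-f).

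- 10 of 70, SD 14.8: shift 12 × 10/70 = 1.71. Variance 219.0 + 17.6 = 236.7, SD 15.4, CI half-width 1.995 × 15.4/√70 = 3.67. Upper limit 5.38, inside 6.
- 30 of 70, SD 14.8: shift 12 × 30/70 = 5.14. Variance 219.0 + 35.3 = 254.3, SD 15.9, half-width 3.80. Upper limit 8.94, outside 6.

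**Probability that the pooled test confirms equivalence (simulation).**

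| Off-target group, shift 12 | SD 5 | SD 8 | SD 10 | SD 14.8 |
|---|---|---|---|---|
| none (70 analysed) | 100% | 100% | 99.7% | 83% |
| 10 of 70 | 100% | 99% | 92% | 63% |
| 8 of 56 (20% loss) | 100% | 96% | 85% | 50% |
| 11 of 55 | 99% | 84% | 67% | 37% |
| 30 of 70 | 5% | 6% | 6% | 5% |

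So the dilution is real for a small group and disappears for a large one. The three ulcer types together must number at least 30, so a shift common to all chronic wounds would rarely slip through.

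**What the by-indication repeat can show.** At n = 10 and SD 14.8 the CI half-width is 2.262 × 14.8/√10 = 10.6 mmHg. An on-target group then lies inside ±6 in 0.4% of trials (about 7% at SD 10, 84% at SD 5). A group 12 mmHg off has a CI wholly outside ±6 in 92, 56, 40 and 21% of trials at SD 5, 8, 10 and 14.8. The composite adds information if the SD is small: its pressure component is met by about 77% of on-target subjects against 12% at a 12 mmHg shift when SD is 5, but by 32% against 23% when SD is 14.8.

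**Would a gate help?** The obvious rule withholds the unqualified conclusion if a one-way ANOVA over closed incisions, dehisced wounds and chronic wounds gives p < 0.10, or if any group's CI lies wholly outside ±6. A flagged trial then keeps the conclusion only for groups whose own CI is inside.

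- Incisions off by 12 (10 of 70): unqualified confirmation falls to 0, 1, 6 and 22% at SD 5, 8, 10 and 14.8.
- One ulcer type off by 12 (10 of 70, chronic wounds 50 of 70): it stays at about 78, 82, 79 and 55%, because the deviant type is averaged inside the chronic group.
- All on target: about 10% of trials are flagged by chance, and unqualified confirmation falls from 83% to 75% at SD 14.8 and from 99.7% to 90% at SD 10.
- Incisions off by 4, inside the margin, at SD 5: 65% of trials are flagged, and in those the group keeps the conclusion about 7% of the time.

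**The case for a change.** The best case for a change is that the text leaves a real gap. Even if the repeat is read as carrying the ±6 rule into each indication, nothing says what a failure does to 11.4, and a CI that straddles a limit has no stated meaning. An unqualified claim with one indication at twice the margin, in over a third of trials at the plan's own SD and subject numbers, is not trivial. A sentence in the SAP costs nothing, and an ANOVA uses all subjects, so it is better powered than a group of 10 alone (66% or more at a 12 mmHg shift in 10 of 70).

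The gap in the text stands. The rest is weaker. A CI not inside ±6 has its ordinary meaning: the null is not rejected for that group. The three-group ANOVA misses a deviant ulcer type; a five-group version would close that hole but would still react to differences inside the margin and still strip conforming small groups of the conclusion.

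The evidence that pressure itself varies by wound is also thin. Section 6.1.1 speaks of dressing changes and therapy length, and describes the pump as holding a nominal 80 mmHg. The remark in 4.2 that "PICO 14 is considered to be clinically interchangeable for the management of chronic wounds" (and the other wounds listed there) concerns the device, so it is neither an admission nor a claim that the wounds themselves are alike.

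**Conclusion.** No change follows. A pooled primary mean with by-indication results beside it is a standard and fair trade-off in a 70-subject single-arm follow-up study with as few as 10 subjects in some indications. The plan already displays what a reader needs to notice a deviant group. A competent report will show the number analysed per indication, describe the combined result as an average over the recruited mix, and treat a wide by-indication CI as inconclusive.

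The possible size of the problem, given a 12 mmHg shift in one indication and none elsewhere, is a pooled pass in about 37-63% of trials at SD 14.8 and 99-100% at SD 5 when that indication holds 1/5 to 1/7 of subjects, and about 5% when it holds 30 of 70. The shift and the smaller SDs are assumptions. The only SD in the documents, 14.8, comes from a sample device, so the spread of subject averages is unknown. Whether to tie the efficacy claim to a heterogeneity pre-test is a choice on which reasonable statisticians differ, and at these group sizes the gate brings false alarms and lost conclusions that offset its benefit.
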